2. BACKGROUND

2.1. Study Disease

As the third leading cause of cancer in both men and woman in the United States, it is estimated that 50,630 people will die from colorectal cancer (CRC) in 2018[1]. The majority of CRC cases are due to spontaneous genetic changes, which can include microsatellite instability (MSI), chromosomal instability (CIN), and the CpG island methylator phenotype (CIMP)[2]. Approximately 15 percent of all CRC (4% in metastatic CRC) are considered microsatellite instability (MSI-high), whereas 85 percent of all CRC cases are microsatellite stable (MSS) or MSI-low. The immune system has long been known to play a role in CRC, where intratumoral immune infiltration has been shown to correlate with improved prognosis[3-11]. While durable objective responses (OR) following T cell checkpoint inhibition in the treatment of refractory solid tumors[12-16] are a proof of principle that endogenous adaptive immune responses can be harnessed by immunotherapy[17-20], no objective clinical responses with anti-PD-1 (nivolumab)[21] or an anti-PD-L1 antibody (BMS936559/MDX-1105)[13] were observed in CRC patients with the rare exception in an MSI-H CRC patient[22].

2.2. Dual Blockade of PD-1 and LAG-3

Lymphocyte-activation gene 3 (LAG-3) is a cell surface molecule expressed on activated T cells, and has a negative regulatory effect on T cell function. While the mechanism by which it modulates T lymphocyte activity is incompletely understood, it has structural homology with CD4 and binds its primary ligand, MHC class II with higher affinity than CD4, thereby mediating a state of T cell exhaustion. Relatlimab (BMS-986016) is fully human monoclonal immunoglobulin (Ig) G4 antibody that binds to a defined epitope on LAG-3 with high affinity and specificity and potently blocks the interaction of LAG-3 with MHC class II, resulting in a reversal of LAG-3-mediated T-cell downregulation.

In preclinical models and early clinical studies, anti-LAG-3 antibodies have demonstrated minimal anti-tumor activity as a single agent but synergistic activity when combined with anti-PD-1 antibody. The combination of the PD-1 inhibitor nivolumab plus the LAG-3 inhibitor relatlimab is being tested in the ongoing phase 1/2a trial CA224020. As of April 2017, 268 subjects had been treated with relatlimab monotherapy (N=25) or combination with nivolumab (N=243), with acceptable safety profile observed at all doses tested. Of 48 evaluable patients in the PD-1/PD-L1 experienced melanoma cohort, an ORR of 12.5% and DCR of 54% was observed [23].

2.3. Relatlimab Dose Selection

Nivolumab was recently approved for use at a dosing of 480 mg flat dosing every 4 weeks in multiple cancers, based on clinical data and population PK (PPK) simulations and exposure-response analyses suggesting no significant impact on toxicity or efficacy. Similarly, a Q4 weekly dosing of relatlimab is highly desirable from an economic standpoint and for patient convenience. The justification for the flat dosing of relatlimab at 160 mg Q4 weekly is based on PPK simulation predicting similar exposure to that seen with Q2W dosing. The safety of relatlimab 160 mg Q4W in combination with nivolumab 480 mg Q4W is being evaluated in the ongoing Phase 1/2a study CA224020, and will be further evaluated in the present study. Please see the Relatlimab Investigator's Brochure for more information regarding experience and safety of nivolumab/relatlimab 160/480 Q4W dose.

2.3.1. Justification for 480 or 960 mg Q4W

The target dose of relatlimab 480 mg Q4W dose is based on the consideration of clinical safety and target engagement will provide meaningful clinical activity. The relatlimab dose was selected after consideration of several factors including relatlimab PK, pharmacodynamics, population pharmacokinetic (PPK) model predicted exposure metrics, benefit/risk assessment of relatlimab and nivolumab co-administration, and extensive nivolumab monotherapy clinical experience.

Safety:

[figure not shown]

[figure not shown]
Please see the Relatlimab Investigator's Brochure for more information regarding experience and safety of relatlimab 480 mg Q4W dose.

2.4. Rationale

Mismatch repair (MMR) deficient tumors, also termed MSI-high, harbor hundreds to thousands of mutation-associated neoantigens (MANAs) that can be recognized and targeted by T cells. Several studies have revealed that anti-CTLA-4 or anti-PD-1 therapies can unleash and amplify preexisting MANA-specific tumor-infiltrating T cells in the tumor and peripheral blood[25, 26]. Data from a phase II trial by Le et al demonstrated that 90 percent of MSI-high patients (9/10) experienced either an objective response or disease stabilization, as compared to only 11 percent of MSS patients (2/18), with disease stabilization being the best response seen in MSS patients[27]. The updated overall response rate (ORR) was 53% in MSI-H CRC[28]. In a separate clinical trial, nivolumab resulted in a 31% response rate and the combination of nivolumab and ipilimumab led to a 55% ORR[29, 30]. One explanation that could account for why some MSI-high patients progress after checkpoint blockade and conversely, why some MSS patients exhibit disease control could potentially be found in the differences in tumor immune microenvironment (TiME).

We recently established that the high density of somatic mutations found in MSI-high CRC tumors exhibit robust IFN γ^{hi} PD-1 hi CD8 $^+$ T cell infiltration that is associated with myeloid expression of the PD-1 ligand, PD-L1, in response to IFN γ production in the TiME[31]. Upregulated expression of several T cell checkpoints, including LAG-3, CTLA-4, and PD-1, suggest that MSI-high CRC tumors trigger an endogenous anti-tumor immune response that is counter-regulated by the expression of a variety of immunoregulatory ligands[31].

This study aims to target immune checkpoints PD-1 and LAG-3 to synergistically improve T cell activation and proliferation by circumventing T cell exhaustion and regulation that promote immune evasion by tumors. This study will be an open label, phase II study to evaluate ORR in patients with metastatic or locally advanced MSS CRC that have a positive and negative CPM score treated with nivolumab and relatlimab.

3. PATIENT SELECTION

3.1. Eligibility Criteria

- 3.1.1. Age ≥ 18 years.
- 3.1.2. ECOG performance status of 0-1 (Appendix A).
- 3.1.3. Patients with histologically proven metastatic or locally advanced microsatellite stable (MSS) colorectal adenocarcinoma.
- 3.1.4. Cohort A: Primary lesion has a composite PD-L1/Mucin (CPM) score $\geq 15\%$.
- 3.1.5. Cohort B: Primary lesion has a composite PD-L1/Mucin (CPM) score < 15%.
- 3.1.6. Cohort C: Prior surgical resection of primary tumor. Prospective biomarker evaluation not required.
- 3.1.7. Patients who have received at least one prior cancer chemotherapy regimen in the locally advanced/metastatic setting. Adjuvant therapy can only be counted if recurrence occurred within 6 months of completing systemic chemotherapy.

- Radiosensitizing doses of chemotherapy are not considered systemic chemotherapy. Patients should be considered for standard therapies.
- 3.1.8. Presence of at least one lesion with measurable disease as defined by 10 mm in longest diameter for a soft tissue lesions or 15 mm in short axis for a lymph node by RECIST 1.1.
- 3.1.9. Patients must have available archival tissue from the surgical resection of their primary tumor for CPM score determination.
- 3.1.10. Patient's acceptance to have a tumor biopsy of an accessible lesion at baseline and on treatment if the lesion can be biopsied with acceptable clinical risk (as judged by the investigator).
- 3.1.11. Life expectancy of greater than 3 months.
- 3.1.12. Patients must have normal organ and marrow function as defined below:

 $\begin{array}{lll} \text{-} & \text{Leukocytes} & & \geq 2,000/\text{mm}^3 \\ \text{-} & \text{Absolute neutrophil count} & & \geq 1,500/\text{mm}^3 \\ \text{-} & \text{Platelets} & & \geq 100,000/\text{mm}^3 \\ \text{-} & \text{Hemoglobin} & & \geq 8.5 \text{ g/dL} \end{array}$

- Total bilirubin $\leq 1.5 \text{ x ULN}$ except subjects with Gilbert's

Syndrome, who must have normal direct

bilirubin

- AST(SGOT) and ALT(SGPT) $\leq 3.0 \text{ x ULN}$ - Albumin $\geq 2.8 \text{ g/dl}$

- Lipase and amylase < 1.5 x ULN Subjects with values > 1.5

ULN may enroll if there are neither clinical nor radiographic signs of a pancreatitis.

- Creatinine $\leq 1.5 \text{ x ULN or creatinine clearance (CrCl)}$

≥ 40 mL/min (if using the Cockroft-Gault

formula below):

Female CrC1 = (140 - age in years) x weight in kg x 0.8572 x serum creatinine in mg/dL

Male CrCl = (140 - age in years) x weight in kg x 1.0072 x serum creatinine in mg/dL

- 3.1.13. LVEF assessment with documented LVEF \geq 50% by either TTE or MUGA (TTE preferred) within 6 months from first study drug administration.
- 3.1.14. Women of childbearing potential (WOCBP) must have a negative serum or urine pregnancy test (minimum sensitivity 25 IU/L or equivalent units of HCG) within 3 days prior to start of study drug. In a case of a positive HCG test, a vaginal ultrasound must be used to confirm a lack of pregnancy. WOCBP is defined in

- **Section 4.8.** WOCBP must agree to follow instructions for method(s) of contraception for the duration of treatment with study drugs plus an additional 165 days (approximately 24 weeks) after the last dose of nivolumab and/or relatlimab. Should a woman become pregnant or suspect she is pregnant while she or her partner is participating in this study, she should inform her treating physician immediately. Men who are sexually active with WOCBP must agree to follow instructions for method(s) of contraception for the duration of treatment with study drugs plus an additional 225 days (approximately 33 weeks) after the last dose of study drug.
- 3.1.15. Patient understands the study regimen, its requirements, risks and discomforts and is able and willing to sign the informed consent form in accordance with regulatory and institutional guidelines must be obtained before the performance of any protocol related procedures that are not part of normal patient care. Subjects must be competent to report AEs, understand the drug dosing schedule and use of medications to control AEs.

3.2. Exclusion Criteria

- 3.2.1. Has known active central nervous system (CNS) metastases and/or carcinomatous meningitis. Subjects with previously treated brain metastases may participate provided they are stable (without evidence of progression by imaging for at least four weeks prior to the first dose of trial treatment and any neurologic symptoms have returned to baseline), have no evidence of new or enlarging brain metastases, and are not using steroids for at least 1 week prior to initiation of study treatment. This is not applicable to patients with primary brain tumors.
- 3.2.2. Patient is expected to require any other form of systemic or localized antineoplastic therapy while on study.
- 3.2.3. Patients with a history of prior treatment with anti-PD-1, anti-PD-L1, anti-PD-L2, anti-CTLA4, or anti-Lag-3 antibodies.
- 3.2.4. Any of the following procedures or medications:
 - Within 2 weeks prior to initiation of study treatment:
 - o Systemic or topical corticosteroids at immunosuppressive doses (> 10 mg/day of prednisone or equivalent). Inhaled or topical steroids, and adrenal replacement steroid doses ≤ 10 mg daily prednisone equivalent, are permitted in the absence of active autoimmune disease.
 - o Palliative radiation or gamma knife radiosurgery.
 - o Chemotherapy
 - Within 4 weeks prior to initiation of study treatment:
 - Any investigational cytotoxic drug. Exposure to any non-cytotoxic drug within 4 weeks or 5 half-lives (whichever is shorter) is prohibited. If 5 halflives is shorter than 4 weeks, agreement with IND Sponsor is mandatory.
 - o Non-oncology vaccines containing live virus.

[figure not shown]
- o Allergen hyposensitization therapy.
- o Growth factors, e.g. granulocyte-colony stimulating factor (G-CSF), granulocyte macrophage-colony stimulating factor (GM-CSF), erythropoietin
- Major surgery
- 3.2.5. History of severe hypersensitivity reaction to any monoclonal antibodies or related compounds or to any of their components (e.g., history of severe hypersensitivity reactions to drugs formulated with polysorbate 80).
- 3.2.6. Uncontrolled intercurrent acute or chronic medical illness.
- 3.2.7. Has an active known or suspected autoimmune disease. Subjects with type I diabetes mellitus, hypothyroidism only requiring hormone replacement, skin disorders (such as vitiligo, psoriasis, or alopecia) not requiring systemic treatment, or conditions not expected to recur in the absence of an external trigger are permitted to enroll.
- 3.2.8. Has a diagnosis of immunodeficiency.
- 3.2.9. Prior tissue or organ allograft or allogeneic bone marrow transplantation. Exceptions can be approved by the IND Sponsor if loss of the graft is not a clinical concern.
- 3.2.10. A known or underlying medical condition that, in the opinion of the Investigator, could make the administration of study drug hazardous to the subject or could adversely affect the ability of the subject to comply with or tolerate study.
- 3.2.11. Patients with a history of interstitial lung disease.
- 3.2.12. Requirement for daily supplemental oxygen.
- 3.2.13. Uncontrolled or significant cardiovascular disease (i.e. cardiomyopathy, congestive heart failure with New York Heart Association (NYHA) functional classification III-IV, pericarditis, significant pericardial effusion, significant coronary stent occlusion), including, but not limited to any of the following:
 - Myocardial infarction (MI) or stroke/transient ischemic attack within the 6 months prior to consent
 - Uncontrolled Angina within the 3 months prior to consent
 - Any history of clinically significant arrhythmias (such as ventricular tachycardia, ventricular fibrillation, or torsades de pointes)
 - QTc prolongation > 480 msec
 - Cardiovascular disease-related requirement for daily supplemental oxygen
 - History of two or more MIs OR two or more coronary revascularization procedures
 - Subjects with history of myocarditis, regardless of etiology.

- 3.2.14. Troponin T (TnT) or I (TnI) >2 x ULN. Subjects with TnT or TnI levels between >1 to 2 x ULN will be permitted if repeat levels within 24 hours are ≤ 1 x ULN. If TnT or TnI levels are >1 to 2 x ULN within 24 hours, the subjects may undergo a cardiac evaluation and be considered for treatment, following a discussion with the IND Sponsor. When repeat levels within 24 hours are not available, a repeat test should be conducted as soon as possible. If TnT or TnI repeat levels beyond 24 hours are ≤ 2 x ULN, the subject may undergo cardiac evaluation and be considered for treatment, following discussion with the IND Sponsor.
- 3.2.15. Has a confirmed history of encephalitis, meningitis, or uncontrolled seizures in the year prior to informed consent.
- 3.2.16. Positive blood screen for Human Immunodeficiency Virus (HIV) (HIV 1/2 antibodies) or known acquired immunodeficiency syndrome (AIDS).
- 3.2.17. Any positive test for Hepatitis B or Hepatitis C virus indicating presence of virus, e.g. Hepatitis B surface antigen or Hepatitis C antibody positive (except if HCV-RNA negative).
- 3.2.18. Has active infection requiring systemic antibacterial, antiviral, or antifungal therapy ≤ 7 days prior to initiation of study drug.
- 3.2.19. Subjects unable to undergo venipuncture and/or tolerate venous access.
- 3.2.20. Any other sound medical, psychiatric, and/or social reason as determined by the Investigator.
- 3.2.21. Patient is, at the time of signing informed consent, a regular user (including "recreational use") of any illicit drugs or had a recent history (within the last year) of substance abuse (including alcohol).
- 3.2.22. Women who are pregnant or nursing.
- 3.2.23. Women with a positive pregnancy test on enrollment or prior to investigational product administration.
- 3.2.24. WOCBP and men with female partners (WOCBP) who are not willing to use contraception.

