Simon two-stage minimax design is planned for each cohort. Initially, 18 patients per cohort will be treated in Stage 1. Patients will be considered evaluable if they receive at least one dose of study drug. If there is at least 1 response in the initial 18 patients in a cohort, then an additional 14 patients will be enrolled in Stage 2 for a total of 32 (18 + 14 = 32) patients in that cohort. If a total of 4 or more responses are observed in Stages 1 and 2 combined, we conclude the regimen is promising and warrants further study. This design has 90% power to reject the null response rate of 5% in favor of 20% response rate, with one-sided type 1 error 0.1.

We expect that the prevalence of a positive CPM score is 10-15% among MSS CRC patients. Therefore, we will need to pre-screen 220-320 MSS CRC patients in order to identify 32 marker positive MSS CRC patients. Assuming 95% of CRC patients are MSS, we will pre-screen a total of 235-340 CRC patients.

The study will consist of a pre-screening period (for Cohorts A and B), a screening period (within 28 days of the first dose), a treatment period, and a follow-up period. Subjects will receive treatment on 28 day cycles, and will come to clinic for dosing and/or assessments on Day 1 of each cycle and additional days for safety and immune monitoring follow up as per the study schedule in **Section 9.** No dose escalations or reductions of nivolumab or relatlimab are allowed. Complete information on study drug administration, schedule, and dosing can be found in **Section 4.1.**

The study will include a safety run-in for the first six patients for Cohorts A and B only. If more than 1 of the first 6 patients experiences an unacceptable toxicity within the first cycle, then enrollment will be halted and the overall risk-benefit ratio of the study will be reconsidered. At any time thereafter, if more than 33% of patients are observed to experience unacceptable toxicity within the first cycle, enrollment will be halted and the safety of the combination will be reevaluated. Complete unacceptable toxicity criteria can be found in **Section 4.7**.

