4.5. Permitted Therapy

Subjects are permitted the use of topical, ocular, intra-articular, intranasal, and inhalational corticosteroids (with minimal systemic absorption). Immunosuppressive agents and the use of systemic corticosteroids are permitted in the context of treating AEs, prophylaxis prior to a diagnostic procedure (e.g., contrast MRI/CT scans) or as specified in **Section 4.2**. A brief course of corticosteroids for prophylaxis (e.g., contrast dye allergy) is permitted.

Subjects may continue to receive hormone replacement therapy (HRT).

Palliative and supportive care for disease-related symptoms may be offered to all subjects on the trial

The potential for overlapping toxicities with radiotherapy and relatlimab ± nivolumab is currently not known. Therefore, palliative radiotherapy is not recommended while receiving any of these drugs, alone or in combination. If palliative radiotherapy in short courses and for isolated fields is required to control symptoms, then drug administration should be withheld, if possible, for at least 1 week before radiation and for at least 1 week after its completion. Subjects should be closely monitored for any potential toxicity during and after receiving radiotherapy. Prior to resuming study drug treatment, radiotherapy-related AEs should resolve to ≤Grade 1 or baseline and subjects must meet relevant eligibility criteria as determined by the IND Sponsor. The IND Sponsor must be consulted prior to re-initiating treatment in a subject with a dosing interruption lasting > 6 weeks after the last dose.

Details of palliative radiotherapy should be documented in the source records and electronic case report form (eCRF). Details in the source records should include: dates of treatment, anatomical site, dose administered and fractionation schedule, and AEs. Subjects receiving palliative radiation of target lesions will have the evaluation of ORR just prior to radiotherapy but such subjects will no longer be evaluable for determination of response subsequent to the date palliative radiation occurs.

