- 2: Cancer history includes: primary site of cancer, gross location of primary tumor, secondary sites of cancer, histology, histologic grade, date of initial diagnosis, date of metastatic diagnosis, prior cancer therapy regimens, MSI testing, and tumor mutation testing.
- 3: Complete physical examination and assessment of ECOG PS will be completed at baseline; focused physical examinations and assessment of ECOG PS will be conducted thereafter. Exams, concomitant medication, AE assessments, and ECOG PS can be evaluated up to 3 days prior to infusion.
- 4: Blood pressure, pulse, and temperature. Vitals will be collected prior to and at the end of the nivolumab/relatlimab infusion (+ 15 minutes).
- 5: Height will be obtained at or prior to baseline only.
- 6: Virology screen: HIV antibody, hepatitis B surface antigen and hepatitis C antibody; additional virology may also be evaluated. Subjects who are hepatitis C antibody positive and confirmed negative viral load at screening will be allowed to enroll.
- 7: Clinical hematology: CBC with differential ANC, ALC, AEC, and platelet count; serum chemistry: sodium, potassium, chloride, bicarbonate, glucose, BUN, creatinine, ALT, AST, alkaline phosphatase, total bilirubin, direct bilirubin, amylase, lipase, total protein, albumin, calcium, magnesium, and phosphorus. LDH at baseline only.
- 8: TSH (Total T3 and free T4 if TSH abnormal and clinically indicated).
- 9: T (cTnt) or I (cTnI). To be obtained on C1D1, C2D1, and C3D1 only. Troponin elevations will require the participant to undergo a cardiac evaluation per **Section 5.2**. Following this evaluation, determination of further treatment will be based on the discussion with the IND Sponsor.
- 10: Bilirubin, blood, glucose, ketones, leukocytes, nitrite, pH, color, protein, RBC and WBC count, and specific gravity.
- 11: Pregnancy tests will be administered to WOCBP: serum pregnancy test is required at screening; serum or urine pregnancy tests are required before doses on Day 1 of dosing weeks.
- 12: Labs may be collected within a window of up to 3 days prior to dosing.
- 13: ECG should be performed at baseline (within 14 days prior to first dose on C1D1), if clinically indicated, or at elevation of troponin levels per **Section 5.2**.
- 14: LVEF assessment with documented LVEF \geq 50% by either TTE or MUGA (TTE preferred test) within 6 months from first study drug administration.

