- 15: Spiral CT of thorax, abdomen and pelvis (and other imaging studies as clinically indicated to evaluate suspected sites of metastatic disease). If a subject cannot have a CT scan (e.g., allergy to contrast dye), an MRI should be performed. On study radiologic evaluations and tumor measurements (RECIST/iRECIST per **Appendix C and D**) will be at baseline, 12 weeks (+/- 2 week), every 8 weeks (+/- 2 week) through week 52, and then every 12 weeks (+/- 2 week) thereafter including the EOT evaluation (± 4 weeks). The EOT scans do not need to be repeated if

- one has been done within the past 6 weeks. Weeks are in reference to calendar week and should not be adjusted due to dosing delays.
- 16: Baseline only (any time prior to the first dose after eligibility is met)
- 17: Whole blood for PBMC, plasma, and serum will be collected at baseline (any time prior to the first dose after eligibility is met), 4 weeks (+/- 1 week), every 16 weeks (+/- 2 week) through week 52, and then every 24 weeks (+/- 2 week) thereafter including the EOT evaluation. Weeks are in reference to calendar week and should not be adjusted due to dosing delays.
- 18: Up to 120cc of whole blood for PBMC isolation will be collected at baseline (any time prior to the first dose after eligibility is met) and at week 4. Up to 150 cc will be collected at subsequent time points.
- 19: Stool, oral wash (and/or buccal mucosal) specimens, and microbiome questionnaire will be obtained when available. All stool specimens should be collected within 72 hours (and ideally within 24 hours) of the patient's appointment. Baseline specimens may be obtained any time prior to the first dose after eligibility is met. On study stool specimens will be obtained every 12 weeks (+/- 2 week) through week 52, and then annually thereafter including the EOT evaluation (± 4 weeks). Oral wash and/or buccal swab will be collected at baseline, once during treatment and annually thereafter including the EOT evaluation (± 4 weeks). Additional samples may be obtained if the patient has any drug-related toxicity at any point during the trial. Detailed instructions for stool and oral wash collection and shipment are provided in the Laboratory Manual.

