APPENDIX B: MANAGEMENT ALGORITHMS

These general guidelines constitute guidance to the Investigator and may be supplemented by discussions with the IND Sponsor. The guidance applies to all immuno-oncology (I-O) agents and regimens.

A general principle is that differential diagnoses should be diligently evaluated according to standard medical practice. Non-inflammatory etiologies should be considered and appropriately treated.

Corticosteroids are a primary therapy for immuno-oncology drug-related adverse events. The oral equivalent of the recommended IV doses may be considered for ambulatory subjects with low-grade toxicity. The lower bioavailability of oral corticosteroids should be taken into account when switching to the equivalent dose of oral corticosteroids.

Consultation with a medical or surgical specialist, especially prior to an invasive diagnostic or therapeutic procedure, is recommended.

The frequency and severity of the related adverse events covered by these algorithms will depend on the immuno-oncology agent or regimen being used.

[figure not shown]

APPENDIX C: RESPONSE EVALUATION CRITERIA IN SOLID TUMORS (RECIST) 1.1 CRITERIA FOR EVALUATING RESPONSE IN SOLID TUMORS

RECIST version 1.1 will be used in this study for assessment of tumor response. While either CT or MRI may be used utilized, as per RECIST 1.1, CT is the preferred imaging technique in this study.

Disease Parameters

Measurable disease: Measurable lesions are defined as those that can be accurately measured in at least one dimension (longest diameter to be recorded) as \geq 20 mm by chest x-ray, as \geq 10 mm with CT scan, or \geq 10 mm with calipers by clinical exam. All tumor measurements must be recorded in millimeters (or decimal fractions of centimeters).

Note: Tumor lesions that are situated in a previously irradiated area might or might not be considered measurable unless there is evidence of progression in the irradiated site. Malignant lymph nodes. To be considered pathologically enlarged and measurable, a lymph node must be ≥15 mm in short axis when assessed by CT scan (CT scan slice thickness recommended to be no greater than 5 mm). At baseline and in follow-up, only the short axis will be measured and followed.

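### The baseline scan may predate chemotherapy or palliative radiation that the 2-week exclusion allows, so the effect of that treatment can enter the primary ORR; a scan-order rule is missing

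*Combined protocol and SAP*

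**What the plan says.** Three timing rules meet here.

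- **Scan window.** Section 1.4 sets "a screening period (within 28 days of the first dose"). In both study calendars (Sections 9.1 and 9.2) the pre-treatment CT/MRI sits in the screening column, which runs from day -28 to day 1. Footnote 15 adds only that evaluations "will be at baseline, 12 weeks (+/- 2 week), every 8 weeks (+/- 2 week) through week 52", so the baseline scan has no tighter limit. The ECG has one: "ECG should be performed at baseline (within 14 days prior to first dose on C1D1").
- **Prior-treatment window.** Exclusion 3.2.4 lists chemotherapy and "Palliative radiation or gamma knife radiosurgery" under the heading "Within 2 weeks prior to initiation of study treatment". Investigational cytotoxic drugs are barred for 4 weeks, and non-cytotoxic drugs for 4 weeks or 5 half-lives, whichever is shorter.
- **Prior-therapy requirement.** Criterion 3.1.7 admits "Patients who have received at least one prior cancer chemotherapy regimen in the locally advanced/metastatic setting". It does not ask for progression on the last regimen, although it adds that standard therapies should be considered.

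Appendix C measures partial response as a 30% fall from the baseline sum of diameters. On irradiated lesions it says "Tumor lesions that are situated in a previously irradiated area might or might not be considered measurable", and then makes an exception where progression at the irradiated site is shown. Section 4.5 covers radiation of target lesions during study treatment: "such subjects will no longer be evaluable for determination of response subsequent to the date palliative radiation occurs".

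**The concern.** The scan may be up to 28 days old, while the two commonest kinds of prior treatment are barred for only the last 14 days. A patient can be scanned early in screening, then receive a chemotherapy dose or radiation to a measured lesion, and still be eligible. Any shrinkage from that treatment is measured against a scan taken before it was given.

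ORR is the primary endpoint. Each cohort is judged alone against a fixed 5% null, so no control arm absorbs the effect. The decision rests on few events: 1 response in 18 to continue and 4 in 32 to call the regimen promising. The protocol already recognises this kind of confounding after treatment starts (Section 4.5) but has no matching rule for the interval between the baseline scan and the first dose.

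**Working it through.** **1. The exposed interval.** Scan age up to 28 days (Section 1.4; calendars) minus a 14-day exclusion (3.2.4) leaves 28 - 14 = up to 14 days, about day -28 to day -15. Investigational cytotoxic drugs fall outside the gap, because their 4-week bar matches the scan window.

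**2. Does another rule order the scan after prior therapy?** Exclusion 3.2.2 concerns therapy expected while on study. Section 4.3 bars concurrent anticancer therapy during the study; if that covered all of screening, the 2-week item would be largely redundant. Section 4.5 applies to radiotherapy during study treatment. The Appendix C note concerns lesions irradiated earlier, not lesions irradiated after baseline. None sets the order.

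**3. Reproducing the design.** With X1 ~ Bin(18, p) and X2 ~ Bin(14, p),

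P(go) = sum over x >= 1 of P(X1 = x) × P(X2 >= 4 - x).

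At p = 0.05:

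- x = 1: 0.3763 × 0.0301 = 0.0113
- x = 2: 0.1683 × 0.1530 = 0.0258
- x = 3: 0.0473 × 0.5123 = 0.0242
- x >= 4: 0.0109

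The total is 0.072. At p = 0.20 the same sum gives 0.901. Both agree with the stated type 1 error of 0.1 and power of 90%.

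**4. Sensitivity to carry-over.** Let c be the chance that a patient is counted as a responder through carry-over alone. It is the product of f (share treated between scan and first dose) and q (chance that this yields a confirmed response). The documents give neither, so all values of c are assumptions. The observed rate becomes p* = 0.05 + 0.95c.

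| c | Example f × q | p* | P(false go) | Expected carry-over responses in 32 |
|---|---|---|---|---|
| 0 | none | 5.00% | 0.072 | 0 |
| 0.5% | 5% × 10% | 5.48% | 0.093 | 0.16 |
| 0.75% | 7.5% × 10% | 5.71% | 0.105 | 0.24 |
| 1% | 10% × 10% | 5.95% | 0.118 | 0.32 |
| 2% | 10% × 20% | 6.90% | 0.173 | 0.64 |

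The stated 0.10 is crossed at c of about 0.65%.

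**5. What a false partial response requires.**

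- *Timing.* Under footnote 15 the first on-study scan is at week 12 (+/- 2). The latest permitted prior treatment is 2 weeks before first dose, so the shrinkage must still show about 12 + 2 = 14 weeks later, or 10 + 2 = 12 at the earliest. Appendix C then requires confirmation at 4 weeks or more, and the next scheduled scan is 8 weeks on, near week 20. (Section 5.2 speaks of an 8-week schedule from first dose; I take the more specific footnote as governing.)
- *Size.* If one irradiated lesion is a share w of the baseline sum, shrinks by a fraction s, and the rest is unchanged, the sum falls by w × s, which must reach 0.30. Even if the lesion disappears (s = 1), w must be at least 30%; at s = 0.5 it must be at least 60%. There must also be no new lesion and no non-target progression.

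**6. The other direction.** If the sum grows by a fraction g between an early scan and first dose, the true fall needed for partial response is 1 - 0.70/(1 + g). For an illustrative g of 10% that is 1 - 0.70/1.10 = 36%, so an old scan can also hide a response.

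**The case against.** The strongest reply is that this is silence on scan order, not a contradiction, and that existing safeguards make a false response unlikely. Much of this stands. The week-12 scan and the confirmation rule should remove most transient chemotherapy effects. The 30% rule applies to a sum of up to five lesions, so radiation to one site matters only if that lesion dominates the sum. At c = 0.5% the false-go probability is still below 0.10. Prior regimens are collected at screening, so affected patients could be found later if dates were recorded.

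One can also argue that a consented patient in screening is already on study, so that 3.2.2 and 4.3 forbid interim treatment. That reading is possible but would leave the 2-week exclusion with little purpose, and a standard-of-care scan could predate consent.

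A reader might infer more than the text supports:

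- *That one or two carry-over responses are to be expected.* One certain false responder placed at random among 32 would give a false-go probability of 0.196, and two would give 0.438. Any misclassified responder would produce the same figures, so they say nothing about how often this gap creates one.
- *That the bias is only upward.* Step 6 shows that it need not be.
- *That Appendix C places no progression condition on irradiated lesions.* It has one, loosely worded.

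What remains is that the windows, followed as written, let the effect of non-study treatment count in the primary endpoint, and that the safeguards are weakest for a dominant lesion irradiated after the scan.

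**Conclusion.** The gap is real and should be closed. Up to 14 days of permitted prior treatment can follow the RECIST reference scan, and no rule removes its effect from ORR. I have high confidence in that reading of the text. It rests on taking the scan's age limit from the screening column, because footnote 15 gives none.

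The size is uncertain and probably modest. A false partial response should be uncommon and would most plausibly come from radiation to a lesion that makes up much of the target sum. The design nonetheless has little slack: false-go probability rises from 0.072 to 0.093-0.173 over an assumed per-patient carry-over probability of 0.5% to 2%, and passes 0.10 at about 0.65%. These figures assume a true ORR of 5%, independent patients and no offsetting growth. The documents do not support a claim that ORR will be materially inflated, or that the 2-week exclusion itself is wrong.

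**What to change.** 1. In footnote 15 of both calendars, require the baseline tumor assessment to be done after the last dose of any prior antineoplastic therapy and after completion of any palliative radiation or radiosurgery, still within 28 days of first dose.
2. In the same place, state that a lesion irradiated after the baseline scan may not serve as a target lesion unless the baseline scan is repeated.
3. For patients already enrolled whose baseline scan preceded their last prior therapy, report ORR with and without them as a sensitivity analysis. This needs the dates of the last prior dose and of any radiation.

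The cost is amendment wording and a few scans scheduled later or repeated; the existing 2-week exclusion already leaves about 14 days for them. Sample size, the decision rule and all washout periods stay as they are. Tightening the Appendix C note on previously irradiated lesions is a separate, optional clarification.
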